**(1) ABSTRACT:**

Significant morbidity, mortality, and related costs are caused by traumatic brain injury (TBI). A simple, effective, and lightweight device worn by athletes or war fighters in the field, designed to mitigate TBI resulting from blast trauma or concussive events, would save lives, and the huge costs incurred for life-treatment of surviving victims. An externally-worn medical device (the Device) that applies mild jugular vein compression according to the principle of the Queckenstedt Maneuver, is being developed by Q30 Sports Science, LLC (Q30). Preliminary research suggests that the Device has the potential to reduce the likelihood of TBI. The currently developed collar (Smith 2009, Smith and Fisher 2011, Smith and Fisher 2011, Smith 2012) has been approved for studies in humans (IRB 2013-2240) and the results indicate safety for use during high demand and maximal exertion activities. Regarding safety, the externally worn collar is meticulously designed to mimic the body's own omohyoid muscle actions upon the jugular veins that will provide similar pressure and volume increases not to surpass that of a yawn or the mere act of just lying down.

This study will investigate the effectiveness of this device in high school athletes playing a non-helmeted sport such as soccer. Athletes participating in this study will be randomly assigned to one of two groups: 1) Device wearing during the season or 2) Non-device wearing during the season. This study will focus on the use and effectiveness of the device solely in females, as male football and hockey players have previously been investigated. All participants will be outfitted with an adhesive patch-like accelerometer (which will be placed behind the ear (*Xpatch-X2 Biosystems* [http://www.x2biosystems.com/x2\\_x\\_patch/](http://www.x2biosystems.com/x2_x_patch/)) which will measure the magnitude of every impact to the head sustained by the athlete. Effectiveness of the device will be determined via differences in longitudinal brain imaging and functional testing following competitive soccer participation. A subset of athletes who report a diagnosed concussion will also receive additional brain neuroanatomical and neurophysiological testing within a week following the diagnosed concussive event. At each of these time points participants will also undergo various neurocognitive assessments outlined below.

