**(6) SELECTION & RECRUITMENT OF PARTICIPANTS:**

We will recruit up to 150 study participants. The participants (age 14-19 years old) will be recruited from a local school district and local sports clubs and teams. Participants will be recruited using a top-down approach. We have gained the consent and the cooperation of the school district administrations. Presentations and letters from the research team will be given to each participating school to detail the participation requirements and study risks.. Questions regarding participation will be answered during the presentations or through e-mail or phone. Participants will be contacted via telephone to further explain the study, answer any additional questions and to enroll them in the study. The participants and parents/guardians who voluntarily agree to participate will be scheduled to complete the pre-participation testing. The participant and parent/guardian will read and sign the “Consent to Participate in a Research Study” form, approved by the Institutional Review Board of Cincinnati Children’s Hospital. If the participant and parent/guardian does not read or sign the form, they will not participate in the study. Once the potential study participants/school teams are identified, they will be allocated to one of two groups: 1) Device wearing during the season or 2) Non-device wearing during the season. This research does not mandate that the participant maintains participation in their sport. The desire to participate in the sporting event is an independent, personal decision separate from the decision to enter into this study. If any athlete chooses to stop participation in the sporting activity then they will also be withdrawn from the study, due to no longer meeting inclusion criteria.

Inclusionary criteria include:

- Female

- Normal healthy volunteer
- Able to provide written consent
- Must be 14 years or older and a participant on a high school soccer team

Exclusionary criteria include:

- Unable to provide written consent
- History of neurological deficits, previous cerebral infarction, or severe head trauma as indicated through pre-season screening:
- Medical contraindications to restriction of venous outflow via the internal jugular veins (known increased intracerebral pressure, metabolic acidosis or alkalosis)
- Glaucoma (Narrow Angle or Normal Tension)
- Hydrocephalus
- Recent penetrating brain trauma (within 6 months)
- Known carotid hypersensitivity

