#### **(8) STUDY PROCEDURES:**

##### **Location I – Brain Imaging-Performed at CCHMC Imaging Research Center**

### **MR imaging data Acquisition**

Magnetic Resonance Imaging (MRI), including sequences outlined in Table 1 are all based on the concept of using magnetic fields and radio waves to make chemical, anatomical and physiological assessments with in the living tissue. This technology has been utilized for diagnostic and research purposes since the early 1980s.

This testing will consist of a minimum of 2 MRI sessions (preseason, and post season) and additional scans following any clinically diagnosed concussions, all inside a 3T scanner at the CCHMC Imaging Research Center. During the acquisition of MR images, the study participants will lie on the scanner table. For most portions of MR acquisition, the study participants will only be instructed to lie still. For other parts of the acquisition, study participants will be asked to answer questions that will assess their cognitive ability and working memory. Participants will be allowed to communicate with the MR operator via an always-on, two-way intercom at any time. In addition, the participants have a hand-held air ball to squeeze in the event that they elect to be removed from the magnet immediately. The study participants have control over their presence in the magnet, which in turn tends to minimize feelings of claustrophobia. As magnetic resonance imaging employs the use of strong magnets, patients will receive a standard preoperative screening questionnaire regarding the potential for ferromagnetic objects within their bodies to ensure their safety during the study. Participants will be screened for MRI specific contraindications such as:

- Braces or permanent metal dental work
- Insulin pump
- Cardiac pacemaker
- Cochlear implants
- Hearing aids
- Aneurysm clips
- Orthopedic pins, wires, screws, or plates
- Any other exclusionary criteria as documented on the MRI safety screening poster included with recruitment materials

Those participants with any aforementioned contraindication may be excluded from the imaging portion of the study but will still be eligible to participate in the rest of the study procedures.

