***Statistical considerations.*** The data analysis will begin with a review of descriptive statistics for all major variables and all major subgroupings of variables in the data set. For the inferential methods, we will use a number of different generalized linear modeling techniques, including linear regression models. All analyses will be conducted using SAS® version 9.3 (SAS Inst, Cary, NC), or Mplus (Muthén, 2007). Initial analyses will be undertaken to inspect data for errors, inconsistencies, and incomplete information. This will include examining the data with simple frequency tables and dot plots for univariate data and scatter plots and multi-way dot plots for bivariate and multivariate data. Data anomalies that cannot be resolved by the Biostatistical/data management team will be sent as queries via

email to the project investigator for clarification and/or correction. During the verification process, outlying values will be corrected if necessary. Incomplete information will be corrected and the project investigator will receive updates. To summarize bivariate relationships among predictors and between predictors and outcomes, Chi-square of Fisher's exact test or Spearman's rank correlation coefficient, will be used, as appropriate. For reporting inferential statistics, such as differences in rates or means, 95 percent confidence intervals will be used extensively to quantify degree of clinical efficacy. Unless otherwise stated, statistical tests are considered two-sided and a .05 significance level is used. All models will be adjusted for potential independent predictor variables but will be limited to the number of predictors we can fit in a regression model while maintaining a valid and reliable model. Candidate predictors include amount of playing time, amount of practice time, previous mTBI, weight, age and height. Collinearity will be examined. Linearity assumptions will be checked and transformations examined. In those cases, a log transformation, polynomial terms, or restricted cubic splines will likely be used to relax the assumption of linearity in the regression models. We will remove the nonlinear terms or transformation only if the nonlinear test is non-significant with a  $p \geq .10$ . Additionally, overly-influential observations and distributional assumptions will be checked. Models will be interpreted graphically, predicted values will be examined, and appropriate significance tests will be utilized.

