**Adverse Events.** During the course of the investigation, injuries consistent with the sports being monitored are expected to occur (E.g. concussion, musculoskeletal injury, bone fractures). Care of all injuries will follow standard of care as directed by the team's athletic trainer and/or the participants treating physician. CCHMC will not be responsible for the medical treatment of any injuries that are not directly related to wear of the Q-collar device. In the case of an adverse event that is determined to be directly related to the wear of the Q-collar during competitive play, the principal investigator will report such event to Cincinnati Children's Hospital Medical Center IRB as any future funding organizations in a manner consistent with the requirements of each organization. As described in the consent, if a participant believes they have sustained an injury as a result of the study then they are instructed to contact the principal investigator or director of social services who in turn will then contact CCHMC IRB and necessary funding institutions, as aforementioned. If a participant sustains an injury during testing they will be referred to the most appropriate medical facility or seek medical attention by the physician/medical specialist of their choice.

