### **(13) RISK/BENEFIT ANALYSIS:**

Participants will be approached for participation via the appropriate method. The purpose and the study protocol will be fully explained in conversation and with the informed consent process.

On the day of the study, the investigators will confirm that the volunteer participant has no health impairment as outlined in the exclusion criteria. Time will be taken to repeat the aims of the study, test protocol, and to answer any remaining questions posed by the participant.

The methods described in this protocol have been used extensively in previous testing in the laboratory. During previous testing, there have been no reported injuries, adverse events or complications. Additionally, the investigators have considered potential risk for injury and have taken additional steps, described in the protocol, to minimize these risks.

Subject participation will be halted should an adverse event while wearing the collar, such as syncope, occur. Any adverse events will be immediately reported. The safety officer will evaluate all adverse events and will determine if early stopping of the study due to safety concerns is warranted. Given the study design and sample, we do not deem futility or efficacy stopping rules are warranted.

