**(17) PAYMENT FOR PARTICIPATION:**

Participants will be compensated for their time and effort in participating in this study. They will receive a \$50 Clincard Mastercard® gift card for completing the first testing session and a \$100 Clincard Mastercard® gift card for completing the final testing session. Participants who sustain a clinically diagnosed concussion will also receive \$50 for each completed session following new concussion diagnosis. Registration in the Clincard payment system

requires a social security number, which will be acquired via a complete W-9 form for each participant.

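### Athletes who choose to stop playing are withdrawn from the study with no provision for the post-season visit, so outcomes can go missing after allocation in ways that may differ by arm

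*Combined protocol and SAP*

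**What the plan says.** Section (6) treats playing as the athlete's own decision, separate from joining the study, and then ties the two together: "If any athlete chooses to stop participation in the sporting activity then they will also be withdrawn from the study". The stated reason is that she no longer meets the inclusion criteria, one of which is membership of a high school soccer team. The device is worn, or not, through the season, so anyone who stops in-season does so after allocation.

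Section (13) has a second exit: "Subject participation will be halted should an adverse event while wearing the collar, such as syncope, occur". It does not say whether the post-season assessment is also cancelled.

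Sections (1) and (2) and the statistical analyses in section (9) rest the evaluation on change from pre-season to post-season. On incomplete data, section (9) says only: "Incomplete information will be corrected and the project investigator will receive updates". It defines no analysis population, missing-outcome method or sensitivity analysis for this trial. The one reference to intention to treat, in the summary of prior work, describes the earlier football study.

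Some provisions point the other way. Section (1) gives athletes with a diagnosed concussion extra follow-up: "A subset of athletes who report a diagnosed concussion will also receive additional brain neuroanatomical and neurophysiological testing within a week". Section (8) allows partial participation for athletes with MRI contraindications, who "may be excluded from the imaging portion of the study but will still be eligible to participate in the rest of the study procedures". Section (17) provides a "gift card for completing the final testing session". None of these extends to an athlete who has been withdrawn.

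**The concern.** An eligibility criterion decides who enters. Here it also decides who remains once the arms are formed, so post-season data come only from athletes who kept playing. That is selection on an event after allocation, and balance at allocation does not protect against it.

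A difference between arms is plausible but not shown. No sham is described, so athletes know whether they wear a collar. The halt in section (13) can occur in the device arm only, and if it is read as ending follow-up, athletes with an adverse event on the collar drop out of that arm's outcome data. Section (12) says that "injuries consistent with the sports being monitored are expected to occur", naming concussion among them. If injury leads some athletes to give up the sport, leaving is related to head impact, which is the exposure under study. The protocol does not state reasons for leaving, so that step is an inference.

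**Working it through.** The documents give no dropout rate, SD, effect size or power calculation, so there is no planned figure to reproduce. The calculation below only illustrates how large the bias could be.

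**Inputs**
- From the documents: up to 150 athletes (section 6); two-sided 0.05 level (section 9).
- Assumed: equal split, 75 per arm; independent athletes; no true effect; one continuous change outcome with SD 1 among completers; completers analysed.
- Varied: *q*, the fraction of an arm that leaves, and *s*, the mean outcome of leavers minus that of completers, in SD.

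**Formulas**
- With the whole-arm mean set to 0, the completer mean is −*q·s*.
- Bias = |*q*₁*s*₁ − *q*₀*s*₀|.
- SE = √(1/*n*₁ + 1/*n*₀), with *n* = 75(1 − *q*).
- Type I error = P(|N(bias/SE, 1)| > 1.96).

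**Worked case: 5% and 15% loss, *s* = 1 in both arms**
- *n* = 75 × 0.95 = 71.25 and 75 × 0.85 = 63.75.
- SE = √(1/71.25 + 1/63.75) = 0.172.
- Bias = 0.15 − 0.05 = 0.10 SD, and 0.10/0.172 = 0.58 SE.
- Type I error = 8.9%.

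**Range**

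| Loss by arm | Shift *s* | Bias (SD) | Type I error |
|---|---|---|---|
| 5% / 7% | 1 in both | 0.02 | 5.2% |
| 5% / 10% | 1 in both | 0.05 | 6.0% |
| 5% / 15% | 0.5 in both | 0.05 | 6.0% |
| 5% / 15% | 1 in both | 0.10 | 8.9% |
| 10% / 20% | 1 in both | 0.10 | 8.7% |
| 5% / 20% | 1 in both | 0.15 | 13.7% |
| 5% / 5% | 1 in one arm, 0 in the other | 0.05 | 6.0% |
| 10% / 10% | 1 in one arm, 0 in the other | 0.10 | 9.0% |
| 20% / 20% | 1 in one arm, 0 in the other | 0.20 | 19.5% |
| equal | same in both | 0 | 5.0% |

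The rows with equal loss show that matching dropout percentages are no reassurance when reasons for leaving differ by arm.

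**Checks**
- If the shift is measured from the whole-arm mean, the completer mean is −*s·q*/(1 − *q*). For 5% and 15% with *s* = 1, bias = 0.15/0.85 − 0.05/0.95 = 0.124 SD and type I error is 11.1%.
- Simulated t-tests (15,000 runs, *s* = 1) gave 9.1% for 5%/15%, 8.4% for 10%/20%, 5.3% for 5%/7%, and 4.9% for equal 10% loss.

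**Precision**

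The difference detectable with 80% power is (1.96 + 0.84) × SE. It is 0.457 SD with no loss, 0.482 SD with 10% loss per arm and 0.511 SD with 20%. Precision is therefore a minor matter beside bias.

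**The case against.** The strongest reply is that the rule is narrow and reads as a safeguard of voluntariness: it covers only an athlete who chooses to give up the sport, within a single season. Athletes with a diagnosed concussion who stay enrolled are followed and may form an analysis group. One who stops wearing the collar but keeps playing is withdrawn by neither rule, so the behaviour most closely tied to the collar is untouched. Nothing in the documents shows that leaving depends on arm. All of this stands, and it limits the likely size of the problem. It does not supply the missing post-season assessment.

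The inputs are also assumed. A 1 SD shift is large, more than twice the 0.457 SD detectable with 75 per arm. The model uses one outcome, whereas the plan has voxel-based imaging and many functional measures. Section (8), under Injury Surveillance, assigns the intervention by team; clustering would enlarge the SE and so shrink the bias in SE units. These points stand, which is why a range is shown.

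It can be argued that the aim concerns athletes while they play and are exposed, so leavers answer a different question. This does not justify the rule. A leaver was exposed until she stopped, and collecting her outcome permits both an as-allocated and a continued-players analysis. Withdrawing her rules out the first for her.

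Finally, the halt in section (13) may not be meant to end outcome visits, and the consent form, which may carry withdrawal terms, was not among the text reviewed. The section (13) point is therefore conditional; the section (6) rule is explicit.

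**Conclusion.** The concern holds. Section (6) removes from the study, rather than only from the intervention, an athlete who chooses to stop playing, and no other section retains her for the visit on which the outcome depends. As-allocated analysis remains possible, but with avoidable missing outcomes.

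Under the assumptions shown, the effect is nil to modest when few athletes leave or leavers resemble each other across arms. It becomes material only if leaving is common, linked to outcome and different between arms. Neither size nor direction can be determined from the plan. This should be changed but is not a fatal flaw. Confidence is medium, because everything about its size depends on rates and reasons that the documents do not give.

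**What to change.** 1. In section (6), replace withdrawal from the study with a statement that an athlete who stops playing, or stops wearing the collar, stays in outcome follow-up. She is invited to the planned post-season visit and analysed in her assigned arm unless she withdraws consent. Naming the collar here makes explicit what the protocol now leaves unsaid.
2. In section (13), state that the halt does not by itself end outcome collection. The clinical halting rule is unchanged.
3. Record the reason for stopping, and tabulate it by arm.
4. In section (9), define the analysis population and a method for athletes who still do not return. For region-of-interest and functional measures, use a mixed model that keeps the pre-season value. With two time points this cannot remove a bias unrelated to baseline, so add a sensitivity analysis shifting missing values by 0 to 1 SD separately in each arm. Section (9) already mentions a repeated measures mixed-model design for reaction time; say there how athletes with only a pre-season value are handled.
5. Keep an analysis of continued players as a sensitivity analysis.

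The cost is protocol and consent wording plus a few lines in the analysis section. The post-season visit and its payment are already planned. The downside is that some retained athletes will have had little exposure, which dilutes the effect slightly. The change has to be made before the season, because a post-season scan that was never taken cannot be recovered.

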#### **(7) PROCESS OF OBTAINING CONSENT**

Once a participant is identified as a potential participant, is contacted by a CCHMC/Sports Medicine representative and verbally agrees to participate, the process to obtain consent will begin. The study coordinator will review the informed consent and the participant will have an opportunity to ask any questions regarding the study and/or the study protocol. At that time, the participant will be given time to decide whether or not they wish to participate and if so, asked to sign the informed consent. Once the signature is obtained, the participant will be given a copy of the consent and testing will commence. At no time will the participant be coerced into participation. Receiving the informed consent prior to enrollment will allow the participants to review the study information prior to participation in the study. This will aid the participant to make an informed, unforced decision regarding election to participate in the study.

Because we will be testing teens, we will be using the Parent Consent Form to obtain both the participant assent and the parent consent. The participants and their parents will be given adequate time to review the study materials and ask questions. If they choose to participate, the patient and parent will sign the IRB approved consent forms. It will be made clear to the patient and their parents that participation in the study is voluntary.

In the event that a parent or guardian will not be present at the scheduled testing appointment, consent/assent forms will be provided ahead of time for review. The coordinator will ensure that all necessary forms have been signed prior to any data collection.

#### **(8) STUDY PROCEDURES:**

##### **Location I – Brain Imaging-Performed at CCHMC Imaging Research Center**

### **MR imaging data Acquisition**

Magnetic Resonance Imaging (MRI), including sequences outlined in Table 1 are all based on the concept of using magnetic fields and radio waves to make chemical, anatomical and physiological assessments with in the living tissue. This technology has been utilized for diagnostic and research purposes since the early 1980s.

This testing will consist of a minimum of 2 MRI sessions (preseason, and post season) and additional scans following any clinically diagnosed concussions, all inside a 3T scanner at the CCHMC Imaging Research Center. During the acquisition of MR images, the study participants will lie on the scanner table. For most portions of MR acquisition, the study participants will only be instructed to lie still. For other parts of the acquisition, study participants will be asked to answer questions that will assess their cognitive ability and working memory. Participants will be allowed to communicate with the MR operator via an always-on, two-way intercom at any time. In addition, the participants have a hand-held air ball to squeeze in the event that they elect to be removed from the magnet immediately. The study participants have control over their presence in the magnet, which in turn tends to minimize feelings of claustrophobia. As magnetic resonance imaging employs the use of strong magnets, patients will receive a standard preoperative screening questionnaire regarding the potential for ferromagnetic objects within their bodies to ensure their safety during the study. Participants will be screened for MRI specific contraindications such as:

- Braces or permanent metal dental work
- Insulin pump
- Cardiac pacemaker
- Cochlear implants
- Hearing aids
- Aneurysm clips
- Orthopedic pins, wires, screws, or plates
- Any other exclusionary criteria as documented on the MRI safety screening poster included with recruitment materials

Those participants with any aforementioned contraindication may be excluded from the imaging portion of the study but will still be eligible to participate in the rest of the study procedures.

